Participants (target n=40) were enrolled and randomly assigned to either the intervention or control group. A randomization schedule was created using random number generator in Microsoft Excel (Microsoft Corporation, Redmond, USA). The study research coordinator created the randomization schedule for 40 potential participants prior to any study enrollment. Group assignment was placed in sealed envelopes to blind study investigators to randomization allocation. Corresponding envelopes were not opened until the participant was enrolled into the study.

Eligibility criteria for this study included: (1) 18 or more years of age, (2) diagnosis of diabetes, (3) current or recently-healed DFU (in the last six months), (4) and able to attend regular exercise classes and two data collection sessions. Exclusion criteria included: (1) medical conditions where aerobic or resistance exercise was contraindicated⁸ (e.g., uncontrolled cardiovascular problems), (2) a score of less than 18 on the Montreal Cognitive Assessment indicating moderate cognitive impairment,⁹ (3) response from primary physician requesting that the participant not engage in exercise, (4) current participation in a regular exercise program (more than 30 minutes, more than 2 times a week).

Study participants were recruited from podiatry and wound care clinics in the metro area using posted recruitment materials. Potential participants were also identified through targeted

mailings to patients in the University of Washington medical system with ICD-10 codes that indicate the presence of a DFU. Interested patients were screened by telephone for initial eligibility and, if eligible to participate, were enrolled and randomized to either the exercise group or the control group. For those randomized to the exercise group, we sent a letter to each participant's primary physician to inform them of participation in the EnhanceFitness program. Physicians were asked to respond if their patient should not engage in moderate, non-weight bearing exercise. Informed consent was obtained from all participants prior to their involvement in the study.

Outcomes

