Feasibility Outcomes. We assessed feasibility outcomes to inform future, large-scale RCT research in this area. The feasibility of conducting a RCT to assess effects of seated exercise in people with DFUs was evaluated using the following parameters: (1) recruitment and retention; (2) adherence to the exercise protocol; (3) participant satisfaction with the exercise program; and (4) presence of serious adverse events. Retention was quantified as the percent of participants that completed the study (i.e., attended both the baseline and 12-week follow up appointments), as well as percent of those who withdrew during the study or were lost to follow-up in each arm. Adherence was quantified as percent of exercise sessions attended by those randomized to the exercise group (out of 36 possible sessions). Satisfaction with EnhanceFitness was quantified as a continuous score on a measure of satisfaction, ranging from 0 (not at all satisfied) to 5 (very satisfied). Finally, presence of serious adverse events (SAEs: adverse outcomes, related or unrelated to the study, such as hospitalizations, emergency room visits, increase in wound size,

and infection, over the course of the study) was quantified as the total number of SAEs reported by participants in each trial arm.

Health Outcomes. We anticipated that exercise might affect many aspects of health and health-related quality of life in people with current or recently-healed DFUs. The following health outcomes were assessed: (1) glycated hemoglobin (HbA1c¹⁰); Five-times sit-to-stand test (5xSTS, a measure of lower extremity strength¹¹); Timed-up-and-go (TUG, a measure of functional mobility¹²); and 30-second biceps curls (a measure of upper extremity strength). We also asked participants to complete a survey comprised of standardized self-reported health measures, including the Patient-reported Outcome Measurement Information System measures of global health (PROMIS-Global 10-item short form),¹³ depression (PROMIS-Depression 4-item short form),¹⁴ fatigue (PROMIS-Fatigue 8-item short form), and physical function (PROMIS-Physical Function 11-item short form).¹⁵ The Activities-Specific Balance Confidence Scale was used to assess balance confidence.¹⁶

Additional variables. Participant characteristics (e.g., age, sex, body-mass index, duration of diabetes) were collected at baseline to characterize the sample and evaluate the comparability between the exercise and control groups.

Procedures

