Participants were asked to come to the University of Washington for two data collection sessions. All study procedures were reviewed and approved by a University of Washington institutional review board (IRB). The study was also registered with clinicaltrials.gov

(registration number NCT03002155). Participants were compensated for their time and participation in the study.

Exercise intervention. EnhanceFitness, an existing, evidence-based exercise program, was the intervention for this study. These group classes were offered at no cost to participants. EnhanceFitness classes were designed specifically for older adults at all fitness levels and may be performed in a seated position. Classes were offered at multiple locations across the Seattle metropolitan region, including community and senior centers, making them a convenient option for participants in the study. Each hour-long EnhanceFitness class incorporated cardiovascular exercise (20 minutes), strength training (20 minutes), and stretching (10 minutes). Evidence suggests that EnhanceFitness improves strength,⁷ and reduces depression³ and falls⁵ in older adults. Participants in the exercise group attended EnhanceFitness classes three times a week for 12 weeks and were contacted regularly to remind them to attend their classes.

Control. Participants in the control group were contacted regularly to remind them to not change their exercise habits (self-reported as less than 30 minutes of activity, less than 2 times a week) while enrolled in the study. They were asked not to start new exercise regimens, or begin a regular exercise program. Any changes in their exercise routines were noted by researchers.

Baseline data collection session. At the baseline session, a study investigator explained the study to participants and obtained informed consent. We then administered a baseline survey and obtained performance measurements. The baseline survey included all self-reported health outcomes as well as demographic and health questions. Following the baseline survey, we

administered the 5xSTS, TUG, and biceps curls to assess each participant's baseline strength and mobility. At the end of the session, participants went to a hospital-based laboratory to have their blood drawn to test for HbA1c.

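### The physician-objection exclusion is described only as a check made after randomisation in the exercise arm, and no rule says how objected participants are analysed

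*Combined protocol and SAP*

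**What the plan says.** In the combined protocol and SAP, the Participants section lists as exclusion criterion 3 a "response from primary physician requesting that the participant not engage in exercise". The list ties this to neither an arm nor a time.

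The same section then gives the order of events. Interested patients were "screened by telephone for initial eligibility and, if eligible to participate, were enrolled and randomized". After that, "For those randomized to the exercise group, we sent a letter to each" participant's primary physician. The letter works by opt-out: "Physicians were asked to respond if their patient should not engage in moderate, non-weight bearing exercise". No letter or equivalent check is described for controls, or for anyone before allocation. Under Procedures, consent is placed at the first visit: "At the baseline session, a study investigator explained the study to participants and obtained informed consent".

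On analysis, the Feasibility Outcomes text ties one measure to randomisation: "Adherence was quantified as percent of exercise sessions attended by those randomized to the exercise group". Attrition is the "percent of those who withdrew during the study or were lost to follow-up in each arm", with no category for physician objection. The presence of SAEs "was quantified as the total number of SAEs reported by participants in each trial arm". The Health Outcomes analysis is a group-by-time repeated-measures ANOVA with two time points and alpha 0.10. The document has no intention-to-treat statement, no analysis or safety population, and no rule for exclusions after randomisation.

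**The concern.** An eligibility criterion should be applied before allocation and in the same way to both arms. By the described process, criterion 3 can be met only by someone already randomised to exercise. An equally unfit control stays in.

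Because an objection is labelled an exclusion, removing the participant is a natural reading of the plan, and nothing rules it out. Even without formal removal, an objected participant who does not return at 12 weeks drops out of a two-time-point repeated-measures ANOVA as it is usually run. Either way the arms analysed are no longer those that randomisation produced. The SAE totals and retention percentages by arm are exposed to the same selection. The stated purpose is to inform and power a larger trial, so the one-arm check could be carried forward.

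**Working it through.** There is no figure in the plan to reproduce. It gives a target of 40 (20 per group) and alpha 0.10, but no objection rate, SD or effect size. Everything else below is assumed.

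**Inputs.** q is the share of the exercise arm objected to and lost: 5%, 10% or 20%, i.e. 20q = 1, 2 or 4 expected. The chance of at least one objection in 20 is 1 − (1 − q)^20 = 64%, 88% or 99%. The pre-post correlation is ρ = 0.6, so in baseline SD units the change score has SD √(2(1 − 0.6)) = 0.894. There is no true effect. With two time points, the group-by-time test is the two-sample t-test on change. The nominal false-positive rate in favour of exercise is 5%.

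**Precision.** The 90% confidence interval half-width is 1.686 × 0.894 × √(2/20) = 0.48 SD.

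**Health outcomes.** Three selection patterns were tried, with 400,000 simulated trials per row:

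- Those lost would have changed worse by D: bias = qD.
- Those lost differ in level but not in change: bias = 0.
- Those lost have the poorest observed baselines: bias = −(1 − ρ)φ(z_q)/(1 − q), because the remaining exercise participants start higher and regress towards the mean.

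| Pattern | q | Bias (baseline SD) | False positives favouring exercise |
|---|---|---|---|
| Worse change, D = 0.5 | 5% | +0.025 | 5.9% |
| Worse change, D = 0.5 | 10% | +0.05 | 7.0% |
| Worse change, D = 1 | 20% | +0.20 | 14.8% |
| Level only | 20% | 0 | 5.0% |
| Poorest baseline | 5% | −0.04 | 3.7% |
| Poorest baseline | 10% | −0.08 | 2.8% |
| Poorest baseline | 20% | −0.14 | 1.7% |

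The correlation matters. Over ρ = 0.4 to 0.8, the false-positive rate runs from about 12.8% to 20.1% for q = 20%, D = 1, and from about 6.6% to 7.8% for q = 10%, D = 0.5. The poorest-baseline bias at q = 20% runs from −0.21 to −0.07, and the half-width from 0.58 to 0.34 SD.

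**SAE totals.** Let k be the SAE rate of those lost relative to the others. If they are not replaced, the expected exercise total falls by qk/(1 − q + qk), whatever the underlying rate:

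| k | q = 5% | q = 10% | q = 20% |
|---|---|---|---|
| 1 | 5% | 10% | 20% |
| 2 | 10% | 18% | 33% |
| 3 | 14% | 25% | 43% |

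If they are replaced, the fall is 1 − 1/(1 − q + qk): 0% at k = 1, and 5%, 9% and 17% at k = 2.

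**Retention.** As an illustration, take 15 completers of 20 randomised to exercise: 15/20 = 75%. Removing 1, 2, 3 or 4 objected participants from the denominator gives 15/19 = 78.9%, 15/18 = 83.3%, 15/17 = 88.2% or 15/16 = 93.8%.

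**The case against.** The strongest reply concerns weight.

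- **The objection rate may be low.** Exclusion 1 (exercise contraindicated) and the requirement to be able to attend classes apply to both arms. The programme can be done seated, and a physician's silence counts as no objection. Nothing in the document supports 20%. This stands: the top of the range is an assumption, and the 5–10% cases are small beside the half-width.
- **The direction is unknown.** This also stands. The analysis tests change, and plausible patterns give positive, nil and negative bias.
- **The SAE shortfall at k = 1 is mechanical.** Fewer people are counted and the rate per person is unchanged. True, and no between-arm SAE test is planned. But the plan reports raw totals, which is where the shortfall shows. The replaced case has no textual basis; it is shown only because replacement is not ruled out.
- **Existing text partly covers the gap.** Adherence uses those randomised, withdrawals are reported by arm, and baseline characteristics of completers and non-completers are compared. An objected participant could be counted as a withdrawal, but the plan does not say so. The completer comparison describes attrition; it keeps nobody in an analysis.
- **Loss from the ANOVA affects every dropout.** Correct. What is particular here is a cause of loss that the design creates in one arm only.
- **The trial is a feasibility study written in the past tense.** The design remedy therefore mainly serves later enrolment and the larger trial. That limits what can be repaired here, but finding such a flaw before a larger trial is a purpose of a pilot.

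**Conclusion.** The concern holds. As written, a trial-wide exclusion can take effect only after randomisation and only in the exercise arm, and no text keeps those affected in the health-outcome, retention or SAE analyses. The document does not say that any physician objected or that anyone was removed, so this is a risk of unknown size.

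Under the assumptions shown, the health-outcome bias is minor when objections are rare. It becomes material only near 20% loss with a clearly worse course among those lost. These are scenarios, not bounds. The SAE and retention effects are more direct, but descriptive. The point should be fixed because the repair is cheap; confidence in its practical importance is medium.

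**What to change.** **For any further enrolment and the larger trial.** Obtain consent, send the physician letter for every otherwise eligible person, and open the allocation envelope only after the response window closes. Criterion 3 then applies before randomisation and identically in both arms. The change concerns timing only; it alters no clinical rule.

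The cost is a short delay and letters for all candidates. To randomise 40 takes 40/(1 − q), about 42, 44 or 50 letters at 5%, 10% or 20% objections, against about 20 now. That is 22–30 extra letters and 2–10 more people consented and screened.

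**For this trial.** Analyse and report all randomised participants in their assigned arm, with SAEs and retention given over the number randomised. State how many physicians objected and what happened to those participants: classes stopped, withdrawn, replaced, 12-week visit attended or not. If there were none, one sentence settles the point. The cost is a paragraph and a few counts.

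This second step has limits, and the report should say so. With no true effect, the bias disappears only if every objected participant has 12-week data. If half do, D(q − (q/2)/(1 − q/2)) remains: 0.024 of 0.05 SD at q = 10%, D = 0.5, and 0.089 of 0.20 SD at q = 20%, D = 1. If none do, all of it remains.

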Study Protocol and Statistical Analysis Plan

Title: Effects of an exercise program for people with diabetic foot ulcers: A feasibility study with outcomes

Registration number: NCT03002155

Document date: Updated 2022-07-07

Aim of study:

This research aimed to address the concerning cycle of deconditioning and disablement in people with DFUs by introducing a seated exercise intervention to improve meaningful health and quality of life outcomes. We examined the feasibility of conducting a randomized controlled trial to assess the effects of 12-weeks of seated exercise in people with DFUs compared to peers who did not exercise. We also assessed physical, physiological, and psychosocial health outcomes in both groups. The exercise intervention in this study was EnhanceFitness,¹ an community-based group exercise program appropriate for people with weight-bearing restrictions due to wound-healing protocols. Numerous studies have been conducted that provide evidence of health benefits associated with participation in EnhanceFitness in older adults, including participants with diabetes.²⁻⁷ We hypothesized that people with DFU who engaged in the fitness program would report high levels of satisfaction, adherence and participation, and a low frequency of adverse events. We also hypothesized that participation in the exercise program would be associated with improvements in key health outcomes as compared to a standard-care control group, who were instructed not to engage in regular exercise (i.e., not to change their current habit of no regular exercise).

Materials and methods

A pilot randomized controlled trial was conducted. Study participants were randomly assigned to a group-based exercise program with a seated option for participation (the EnhanceFitness intervention, described below) or to the control group. Participants in the exercise group attended fitness classes for a 12-week period; those in the control group received standard care, which did

not include exercise. Both groups of participants were assessed at two time points, baseline and 12-week follow-up.

Participants

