12-week data collection session. At the 12-week session, we administered a follow-up survey to assess changes in the previously listed self-reported health outcomes. The survey also included questions to assess satisfaction with the EnhanceFitness intervention for participants in the exercise group. Following the survey, we asked participants to perform the 5xSTS, TUG, and biceps curls. At the end of the session, the participant returned to the laboratory to have their blood drawn and tested for HbA1c.

Analysis

Sample Characteristics. Descriptive statistics (mean, standard deviation, frequency distributions) were calculated for variables used to characterize the sample (e.g., participant characteristics). Student *t*-tests (numeric data) and Chi-square tests (nominal data) were used to compare the intervention and control groups based on participant characteristics. The alpha level for these tests was set at $\alpha=0.05$ and significant findings for sample variables indicate that there are differences in demographic or clinical characteristics (e.g., age, sex, duration of diabetes) between the exercise and control groups.

Feasibility Outcomes. The ability to meet recruitment targets (20 participants per group, 40 total) was assessed. Retention (or percent of participants that completed the study) and percent attrition was calculated and reported separately for the intervention and control groups. Pre-intervention

characteristics were compared between participants who did and did not complete the study to determine if there was a biasing effect. Adherence to the protocol was assessed in the intervention group to quantify the extent to which participants attended exercise classes. Satisfaction with EnhanceFitness was assessed in the intervention group to ensure that participants reported a minimum of 4 on a 5-scale measure of satisfaction with the exercise intervention.

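### Wound enlargement is counted within one participant-reported SAE total per arm, with no wound measurement described to verify it and no separation from hospitalization

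*Combined protocol and SAP*

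**What the plan says.** The Aim of study section hypothesizes "a low frequency of adverse events" among those who exercise. Under Outcomes, Feasibility Outcomes, SAEs are the last of four feasibility parameters. They are described by examples, "such as hospitalizations, emergency room visits, increase in wound size" and infection, whether or not related to the study, at any time during follow-up. Their presence "was quantified as the total number of SAEs reported by participants in each trial arm".

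Participants were "assessed at two time points, baseline and 12-week follow-up". At the first session, "We then administered a baseline survey and obtained performance measurements", and "The baseline survey included all self-reported health outcomes as well as demographic and health questions". At the second, "At the 12-week session, we administered a follow-up survey to assess changes in the previously listed self-reported health outcomes", with satisfaction questions added for the exercise group. Both sessions also include the five-times sit-to-stand test (5xSTS), timed-up-and-go (TUG), biceps curls and a blood draw for HbA1c.

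The Participants section admits people with an open ulcer and people whose ulcer healed within the previous six months.

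**The concern.** An increase in size is a comparison of two sizes. The plan counts such increases but describes neither size, so it gives no means of confirming a reported enlargement or finding an unreported one. The only stated source is the participant, who knows whether he or she is exercising. Someone told to exercise on an ulcerated foot may watch the wound more closely, or may play down a change. Either could move the count in one arm only.

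The summary adds a second difficulty. With one total per arm, a slight enlargement and a hospital admission each add one. The reader cannot tell which type of event makes up the total, or how many participants it comes from.

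Eligibility is defined by the foot ulcer, and the feasibility results are meant to inform a larger trial. A low total could mean that wounds did not worsen or that worsening was not reported, and the plan as described cannot separate the two.

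**Working it through.** The plan states no SAE rate, threshold or sample-size figure for safety, so there is no figure of its own to reproduce. The main check is to set the sections side by side.

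| Section | What it supplies on wound size |
|---|---|
| Outcomes, Feasibility Outcomes | Enlargement is an SAE example; source is participant report; summary is one total per arm; no definition of an increase |
| Outcomes, Additional variables | Named examples are age, sex, body-mass index and duration of diabetes; no wound size |
| Baseline data collection session | Consent, survey, 5xSTS, TUG, biceps curls, HbA1c; no wound measurement |
| 12-week data collection session | Survey, the same three tests, HbA1c; no wound measurement and no SAE item named |
| Analysis, Feasibility Outcomes | Recruitment, retention, adherence, satisfaction; SAEs not mentioned |
| Participants | Sealed envelopes conceal allocation until enrollment; nothing on blinding afterwards |
| Exercise intervention; Control | One arm attends classes, the other is reminded not to change its exercise habits, so both know their arm |

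**1. Verification.** No measurement, photograph, examination, chart review or threshold appears in any section. For a participant whose ulcer had healed at entry there is no starting size either, so an increase is undefined and recurrence is not mentioned.

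**2. Differential reporting (illustration; all rates and event numbers assumed).** Expected reported events = true events × proportion reported.

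- Equal truth, unequal reporting: 5 × 0.5 = 2.5 against 5 × 0.8 = 4.0, an apparent gap of 1.5 events.
- The gap equals true events × (0.8 − 0.5). With 2 true events per arm it is 2 × 0.3 = 0.6; with 10 it is 10 × 0.3 = 3.0. With equal reporting it is zero.
- A real difference can also disappear: 8 × 0.5 = 4.0 against 5 × 0.8 = 4.0 hides 3 additional enlargements.

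**3. Pooling.** The text does not say whether linked events count once. An enlargement that becomes infected and leads to an emergency visit and an admission could score up to 4. A total of 4 might therefore be one participant with one episode or four participants with one event each.

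**4. A figure that does not measure the problem.** For no events among n participants, the exact two-sided 95% upper limit is 1 − 0.025^(1/n). With the target of 20 per arm this is 1 − 0.025^(1/20) = 16.8%. If only 10 per arm had an open ulcer (assumed), it is 1 − 0.025^(1/10) = 30.8%. Perfect measurement would give the same limits, because they depend only on n. The one relevant remark is that, with self-report, the limit bounds reported and not actual enlargement.

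**The case against.** The strongest reply is that this is a small pilot, in which SAEs are one of four feasibility parameters and are summarized descriptively. No between-arm SAE test, safety threshold or wound-healing hypothesis is stated. Distorted reporting would therefore affect a descriptive count and would not bias a planned inference. This stands, and it limits the consequence.

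Three stronger readings are tempting, and the documents do not support them.

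- A reader might infer that wound enlargement is the trial's key safety event. The plan gives it as one of four unranked examples. Its importance is a reasonable judgment about this population but is not stated.
- A reader might infer that wound events rest on participants' impressions alone. The text says only that participants reported them. Recruitment ran through podiatry and wound care clinics and a medical system, so a participant could pass on a clinician's measurement. The unitemized health questions at baseline might also touch on the wound. No such source, check or matching 12-week item is described, so the supportable statement is that verification is not described.
- A reader might conclude that two clinic measurements should replace participant report. They would miss a wound that grew and then shrank, leave out recurrence after healing, and count measurement noise as enlargement if no threshold were set. Participant report covers the whole of follow-up and should stay.

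It can also be said that a stated total does not forbid a breakdown by type. That is true, but the total is the only summary the plan commits to.

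**Conclusion.** The concern holds in a limited form. As described, wound worsening is unverified, comes from participants who know their arm, and is merged with hospitalization in one count per arm. The pilot remains usable, but its wound-safety result cannot be interpreted as planned. The point is worth acting on and is not critical.

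The size is not known. The 2.5 against 4.0 example shows only that a gap can arise without a true difference. It rests on assumed reporting rates and an assumed 5 enlargements per arm. The documents do not show that reporting did differ by arm, or in which direction. The 17% upper limit for 0 of 20 should not be cited as an effect of self-report: it reflects sample size, and applies to enlargement only if all 20 had an open ulcer.

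**What to change.** 1. **Reporting.** Replace the single total with counts by type: wound enlargement or recurrence, infection, emergency visit, hospitalization. For each type and arm, give the number of events and the number of participants with at least one. Label wound events as self-reported unless verified. This needs no new data collection beyond the reports already held.

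2. **Verification, where records can be released.** Abstract ulcer sizes from existing clinic notes in both arms, using the same time window around baseline and week 12 and a threshold for enlargement fixed before the sizes are examined. Also record any interim enlargement or recurrence, including in participants whose ulcer had healed at entry. Use these data to verify participant reports, not to replace them, and report the number with missing sizes in each arm.

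The second step requires no extra visit or procedure and could be done retrospectively. It does require permission to release records from several clinics, and some sizes will be missing; that notes hold sizes near both dates is an assumption. Clinic-visit frequency may differ by arm, so some differential ascertainment could remain. If records cannot be obtained, the first step should still be taken.

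### SAE presence is measured only as an event total per arm; the plan does not specify the number or percent of participants affected

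*Combined protocol and SAP*

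**What the plan says.** The Aim of study section hypothesises, for people who take part in the fitness program, "a low frequency of adverse events". It gives no denominator and no threshold.

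Outcomes, Feasibility Outcomes lists four parameters meant to inform a later large RCT, the last being "and (4) presence of serious adverse events". SAEs there include events whether or not related to the study, "such as hospitalizations, emergency room visits, increase in wound size" and infection. The measure of this parameter reads "over the course of the study) was quantified as the total number of SAEs reported by participants in each trial arm".

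The same section defines retention at participant level: "Retention was quantified as the percent of participants that completed the study".

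Analysis, Feasibility Outcomes covers recruitment ("The ability to meet recruitment targets (20 participants per group, 40 total) was assessed"), retention and attrition, a comparison of completers with non-completers, adherence and satisfaction. It does not mention SAEs. Analysis, Health Outcomes does not mention them either. Nowhere is there a rule for repeated or linked events.

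**The concern.** Presence is a yes/no property of a person, whereas the stated measure counts events. The two agree only when nobody has more than one event.

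That condition is doubtful in this population, given the list of examples. A wound that enlarges, becomes infected, and leads to an emergency visit and then admission is one clinical episode in one person, yet it touches all four listed items. Without a counting rule it may add one event to the total or four. Arms with the same number of people affected could therefore show different totals, and arms with equal totals could differ in people affected. This holds even with 20 per arm and complete follow-up.

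At stake is how usable one of the four feasibility parameters will be. A reader who wants to know how often participants were affected cannot learn it from the total.

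**Working it through.** **Inputs.** From the documents: planned arm size n = 20 (Analysis, Feasibility Outcomes); the SAE measure is an event total per arm, and four example event types are listed (Outcomes, Feasibility Outcomes). Assumed, because the documents give no SAE counts: the event total T. The plan states no SAE figure to reproduce.

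**Step 1: one episode, using the plan's own list.** If one person has all four listed items in one episode and each is counted, T = 4 and 1/20 = 5% of the arm is affected. If four people have one item each, T is again 4, but 4/20 = 20% are affected.

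**Step 2: general range.** With T events (T from 1 to 20) in an arm of 20, the number of people affected, x, can be anything from 1 to T.

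- T = 0 or 1: x is known exactly, so there is no gap.
- T = 3: x from 1 to 3, or 5% to 15%.
- T = 6: x from 1 to 6, or 5% to 30%. If nobody has more than four events, x is at least ceil(6/4) = 2, and the range is 10% to 30%.

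For T = 6, events per participant is 6/20 = 0.30 in every case, so that rate cannot tell these situations apart.

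**Step 3: precision of the percent affected.** The exact (Clopper-Pearson) 95% limits are the 0.025 quantile of Beta(x, n − x + 1) and the 0.975 quantile of Beta(x + 1, n − x); the lower limit is 0 when x = 0.

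| x of 20 | Percent | Exact 95% interval |
|---|---|---|
| 0 | 0% | 0 to 16.8% |
| 1 | 5% | 0.1 to 24.9% |
| 2 | 10% | 1.2 to 31.7% |
| 3 | 15% | 3.2 to 37.9% |
| 6 | 30% | 11.9 to 54.3% |

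The intervals are wide and overlap. The participant-level summary measures the right thing, but it is not precise.

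**Step 4: effect of unknown status.** Suppose 3 of 20 are known to be affected and SAE status is unknown for 4 (both assumed). The reported percent is 3/20 = 15%, and the true value could be as high as 7/20 = 35%.

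**The case against.** The plan does define an SAE measure, by arm. Event totals and people affected are both legitimate summaries, and choosing one does not make the other wrong. No SAE test, threshold or progression rule exists, so nothing planned would come out differently. The feasibility measures also follow no single standard: adherence is a percent of sessions and satisfaction is a score. If SAEs are as infrequent as hypothesised, the gap may be small. The 5% end of the six-event example needs one person to have all six events within 12 weeks.

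Most of this stands, and it limits the weight of the point. It does not remove the mismatch between the outcome as named and the quantity counted.

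Three stronger readings are tempting, and the documents support none of them:

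- *A reader might infer that the number affected will go unreported.* The documents contain no results and do not rule out reporting it. They show only that it is not specified.
- *A reader might infer that no frequency can be obtained.* Events per participant follows from the total and the arm size. What cannot be obtained is the frequency of affected participants.
- *A reader might infer that the sample size of the later trial is compromised.* Analysis, Health Outcomes ties powering a larger RCT to the health-outcome results. Nothing links SAEs to sample size, so a projection to a larger trial has no basis here.

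**Conclusion.** The point holds as a modest gap in specification. The outcome is named as presence, measured as an event count, and not supplemented by any participant-level summary in the Analysis section. Following the stated measure does not show how many people were affected.

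The size depends on the unknown total. In an arm of 20, the percent affected is undetermined between 5% and 15% for an assumed 3 events, and between 5% and 30% for an assumed 6. It is fully determined for 0 or 1. The illustration assumes the planned 20 per arm and that one person can contribute several events, which the definition allows. No stated decision changes, so this is a cheap improvement and not an error that undermines the trial.

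**What to change.** In Outcomes, Feasibility Outcomes, and again in Analysis, Feasibility Outcomes, add wording such as:

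> For each arm we report the total number of SAEs and the number and percent of randomised participants with at least one SAE. Linked items arising from one episode count as one event in the total. These summaries are descriptive and no test is made.

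An exact 95% interval for the percent is optional; a plain n (%) is enough for a pilot of this size. The counting rule does not replace the participant-level figure, because one person can still have two separate episodes.

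**Cost.** Two or three sentences, a tally by participant of SAEs that participants have already reported, and a judgement on which items belong to one episode. The document describes the study in the past tense, so the change affects reporting only and asks for no new data.

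**Downside.** The Procedures section does not describe how SAEs were elicited or whether they were tracked in people who left. If SAEs among dropouts are unknown, the percent should be labelled a lower bound. It will also be imprecise with 20 per arm. Keeping the event total beside it loses nothing.
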